7. STATISTICS AND DATA ANALYSIS

We will use the data collected to investigate the specific determinants of AF mechanism and electrophenotype. Patients will be classified into a range of AF mechanisms and electrophenotypes, ranging from organised AF sustained by localised drivers through to disorganised AF. The specific functional (e.g. atrial

conduction properties), structural (e.g. left atrial fibrosis burden) and clinical (e.g. AF duration) determinants of the AF electrophenotype will be investigated.

Intracardiac EGM data and 252 lead ECG

The 252 electrode device data will be analysed using a combination of established signal processing (dominant frequency, phase mapping and Shannon entropy) and machine learning techniques (unsupervised learning to cluster data into distinct phenogroups. For the subset of 10 patients with MRI data, we apply our 'in house' inverse solution and Tikhonov regularisation steps to reconstruct the epicardial electrograms.

Cardiac MRI

I will analyse burden of fibrosis and fibrosis distribution patterns and correlate these with the electrogram data.

AF electrophenotype will be determined using the analyses above. I will characterise each patient using both a regional and a global approach. The regional approach will analyse each sequentially collected 'kernel' of data from the RA and LA and assign a metric of organisation. The electrophenotype of a single patient therefore will be described by the number of organised/disorganised sites. The global approach will assign a global metric of organisation, including data from all collected kernels from both RA and LA. I will investigate the determinants of electrophenotype by correlating electrophenotype with clinical parameters including AF duration, co-morbidities and left atrial size on echocardiography. I will also compare intracardiac mapping pre- and post- PVI to investigate the impact of PVI on AF electrophenotype. I will investigate the degree to which the AF electrophenotype can predict outcomes compared to conventional clinical and echocardiographic predictors.

Biomarkers for identification of AF electrophenotype

We will look for differences in lipid metabolite levels, miRNA and protein expression between the electrophenotype groups, which may serve as biomarkers to non-invasively distinguish between these groups. I will analyse human serum using DNA barcode technology integrated with a nanopore platform to measure levels of these circulating miRNAs and proteins. Machine learning has been used effectively in proteomic studies (30). I aim to apply the biomarker data with electrical and imaging data using unsupervised machine learning to identify clinically relevant clusters (phenotypes).

Developing non-invasive methods to classify AF electrophenotype

Using simultaneously collected 252 lead ECG and intracardiac data, together with CMR LA fibrosis data, the surface ECG and biomarkers, I will develop tools to non-invasively classify AF electrophenotype.

Using the intracardiac data as the gold standard, I will continue to develop tools to determine the degree of global fibrillation organisation from surface ECGs, using band-power feature analysis and machine learning techniques. 252 lead ECG-derived biatrial maps in atrial fibrillation will then be analysed using both established (dominant frequency, phase mapping and Shannon entropy) and the novel (ML based analysis, including unsupervised machine learning) to further stratify patients into a spectrum of organised to disorganised electrophenotypes. Simultaneous

intracardiac and 252 lead ECG recordings will also allow further validation of 252 lead ECG in atrial fibrillation. I will use CMR data to correlate electrophenotype with anatomical data. LA fibrosis will be categorised by both degree and distribution of fibrosis and correlated with both intracardiac and non-invasively acquired electroanatomical data using linear regression models and ML. Invasive and non-invasive parameters will be combined and correlated with AF recurrence to create a tool using only non-invasive data to determine a patient-specific electrophenotype.

Outcomes

Freedom from AF, AF burden and quality of life outcome data will be correlated with electrophenotype groups (as defined by the above analyses) to investigate if certain groups benefit more from ablation than others.

Sample size is based on collecting sufficient data to detect differences in electrophenotypes using biomarkers and ECG parameters.

Data will be analysed by the chief investigator and the research team at the National Heart and Lung Institute, Imperial College London.

Data and all appropriate documentation will be stored for a minimum of 10 years after the completion of the study, including the follow-up period.

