Lastly, CMR has been used to quantify LA fibrosis (26), and based on our groups work in VF showing the important role of fibrosis pattern on determining VF mechanism (19), LA fibrosis maps from CMR may therefore be useful in complementing ECG and ECGI in helping to classify an individual's AF mechanism and electrophenotype. Our own analyses have described the distribution of scar within the left atrium and the effect of fibrosis on left atrial electrophysiological properties, with recent demonstrations that LA fibrosis as detected on CMR correlates with intracardiac electrograms voltage acquired in atrial fibrillation (27).

Recurrence of atrial arrhythmia after AF ablation

Current success rates following ablation for PsAF are only 50%. A significant proportion of these recurrences are due to the organised atrial arrhythmias atrial flutter and atrial tachycardia. Atrial flutter may be cavotricuspid isthmus (CTI) dependent or have a different mechanism. Ablation for CTI dependent flutter has a significantly higher success rate compared to ablation for atrial tachycardia. Additionally, knowledge of the tachycardia mechanism can be helpful to plan an ablation procedure; if the tachycardia originates in the right atrium the procedure can be undertaken under local anaesthetic without a transeptal puncture, while a left atrial tachycardia may require a general anaesthetic and transoesophageal echocardiography for transeptal puncture.

Biomarkers for atrial fibrillation

Proteomics profiling has been used to identify proteins independently associated with incident AF (28). MicroRNAs have similarly been associated with incident AF and cardiac remodelling (29). Machine learning (ML) has been incorporated with proteomics to yield new insights and outperform traditional techniques (30).

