1.2. Rationale for current study

1. In human AF, there is a spectrum of different AF mechanisms (manifest as a

- spectrum of 'electrophenotypes') that can sustain AF
2. The specific AF electrophenotype in each patient is determined by the underlying atrial substrate, and correlates to functional (e.g. conduction velocity), structural (fibrosis burden) and clinical characteristics (e.g. AF duration)
 3. Analysis of surface ECGs, 252 lead ECGs and scar maps from MRI, in isolation or in combination, can provide an accurate non-invasive classification of AF electrophenotype, when compared to the gold-standard classification using intracardiac electrograms
 4. Machine learning (ML) can be applied to ECGs, electrograms, 252 lead ECG and cardiac MRI to aid classification of electrophenotype

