3. STUDY DESIGN

This is a prospective interventional study investigating invasive and non-invasive tools for determining AF electrophenotype. The study will last 2 years in duration and will recruit patients undergoing ablation or DCCV procedures for atrial fibrillation (AF). Patients will be recruited from secondary care clinics or pre-assessment prior to procedures at Hammersmith Hospital.

The study will be run at a single centre at the Hammersmith Hospital, Imperial College Healthcare NHS Trust. We will aim to enrol 300 patients.

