3.2. Study protocol

Patients that suffer from AF and have been put forward for an ablation or DCCV, on clinical grounds as per current guidelines, will be recruited. Patients will be approached by a member of the clinical team by telephone from the Hammersmith Hospital waiting lists to discuss their interest in participating in the study. If the patient is interested, they will be provided with a patient information sheet, detailing information with regards to the study. The Investigators will subsequently consult with these patients to explain the study in greater detail and answer any further questions, in person, during an outpatient clinic visit or by phone. The consent form will include all information about the study and the mapping procedure.

All patient clinical data will be collected on a standardised electronic case report form.

Study groups

Diagram summarising study subgroups:

Biomarker protocol (all groups):

All patients will have blood samples taken to investigate for biomarkers that may correlate with electrophenotypes. In most cases this will be taken during the same blood draw as blood tests taken for clinical care or from sheaths in central veins that are placed routinely during an AF ablation. Rarely it may be necessary to perform an additional venepuncture in order to obtain the samples.

252 lead ECG protocol (green + orange groups):

A subgroup of 50-100 patients with persistent AF will have a 252 lead ECG. This will consist of up to 252 electrodes attached to the patient's front and back. A recording of up to 10 minutes will be taken before the AF ablation or DCCV procedure.

MRI protocol (orange group):

A subgroup of 10-30 patients who are undergoing ablation will undergo thoracic and cardiac MRI including administration of gadolinium intravenously. This will be performed on the day of their ablation procedure, prior to the ablation. This subgroup will have an additional 1-2 visits 1-2 weeks apart prior to their procedure date, where they will attend the hospital for 10 minutes of data collection with the 252 electrode device. This subgroup will have co-registration of the 252 electrode recordings taken on the day of the ablation with the MRI to allow reconstruction of the epicardial

electrograms through the inverse solution and Tikhonov regularisation steps.

DCCV protocol

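### Section 7 categorises left atrial fibrosis by degree before the regression and ML models, with no cut-points given, although fibrosis is elsewhere a measured burden and the MRI subgroup is at most 30 patients

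*Combined protocol and SAP*

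**What the plan says.** Only one sentence in the plan names a model for fibrosis. It stands in section 7, under the heading on developing non-invasive methods to classify the electrophenotype, and it names machine learning as well: "LA fibrosis will be categorised by both degree and distribution of fibrosis and correlated with both intracardiac and non-invasively acquired electroanatomical data using linear regression". It does not say how many categories of degree there will be, where they are cut, how they are coded, or why they are needed.

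Elsewhere fibrosis is a quantity:

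- Section 1.1: "CMR has been used to quantify LA fibrosis".
- Section 1.2 expects that the electrophenotype "correlates to functional (e.g. conduction velocity), structural (fibrosis burden) and clinical characteristics (e.g. AF duration").
- The opening of section 7 gives as its example of a structural determinant "structural (e.g. left atrial fibrosis burden").
- Section 7, Cardiac MRI: "I will analyse burden of fibrosis and fibrosis distribution patterns and correlate these with the electrogram data". This sentence mentions no categories and names no model.

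Fibrosis is measured only in the MRI subgroup. Section 3.2 sizes it thus: "A subgroup of 10-30 patients who are undergoing ablation will undergo thoracic and cardiac MRI". Section 7 has a single figure: "For the subset of 10 patients with MRI data". The whole study is to enrol 300 patients (section 3). No alpha, power, correlation or other effect size is stated for the fibrosis analysis.

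**The concern.** Linear regression accepts a measured burden directly. Cutting burden into categories of degree first treats all patients within a category as alike, which weakens the estimated relation and lowers the chance of detecting a real one. This happens in the study's smallest subgroup, where information is scarcest. With no cut-points written down, the split can also be chosen after the electrogram data are known, and the result may depend on that choice.

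The concern is with degree only. Distribution is a pattern and is naturally categorical. The concern is also with fibrosis as a predictor, not with how patients are grouped by electrophenotype.

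**Working it through.** **No figure to reproduce.** The plan states no power or effect size for this analysis, and the total of 300 comes without a calculation. What follows is an illustration under assumptions.

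**Inputs from the documents.** n = 10 to 30 (section 3.2) and n = 10 (section 7).

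**Assumed inputs.** One fibrosis value and one organisation value per patient, bivariate normal; two-sided alpha 0.05; true correlation ρ from 0.2 to 0.8; no dropout; groups as nearly equal in size as n allows.

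**Continuous burden, by formula.** Power ≈ Φ(atanh(ρ)·√(n−3) − 1.96). With ρ = 0.5, atanh(0.5) = 0.549:

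- n=30: Φ(0.549 × 5.196 − 1.96) = Φ(0.894) = 81%
- n=20: Φ(0.549 × 4.123 − 1.96) = Φ(0.305) = 62%
- n=10: Φ(0.549 × 2.646 − 1.96) = Φ(−0.507) = 31%

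Simulating the t-test of the regression slope gives 83%, 65% and 33%, so the approximation runs slightly low.

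**Categorised burden, by simulation** (20,000 data sets per setting). Ordered groups are scored 1, 2, 3 and so on and tested for trend. Unordered groups are tested with an F test.

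| n | ρ | Continuous | Median split | 3 ordered | 4 ordered | 4 unordered |
|---|---|---|---|---|---|---|
| 10 | 0.3 | 13% | 10% | 11% | 11% | 8% |
| 10 | 0.5 | 33% | 20% | 25% | 27% | 14% |
| 20 | 0.5 | 65% | 42% | 52% | 56% | 36% |
| 30 | 0.3 | 36% | 24% | 29% | 31% | 20% |
| 30 | 0.5 | 83% | 61% | 71% | 75% | 56% |

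**Hand check of the median split.** For normal data, a split at the median multiplies the correlation by √(2/π) = 0.798, so 0.5 becomes 0.399. At n=30, Φ(0.4225 × 5.196 − 1.96) = Φ(0.235) = 59%, close to the simulated 61%.

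**Where continuous power is near 80%.** The correlation needed is ρ = tanh((1.96 + 0.842)/√(n−3)), which is 0.79, 0.59 and 0.49 at n = 10, 20 and 30. The losses there, in percentage points, are:

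| Form of fibrosis degree | n=10 | n=20 | n=30 |
|---|---|---|---|
| Median split | 31 | 24 | 22 |
| 3 ordered groups | 17 | 12 | 11 |
| 4 ordered groups | 11 | 8 | 7 |
| 4 unordered groups | 43 | 29 | 27 |

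**Whole grid** (n = 10, 20, 30; ρ from 0.2 to 0.8). The loss runs from about 1 to 32 points for a median split, 0 to 17 for three ordered groups, 0 to 12 for four ordered groups, and 0 to 43 for unordered groups. It is small at both ends: when power is already very low (n=10 with ρ of 0.2 or 0.3, at most about 5 points) and when it is close to 100% (n=30, ρ = 0.8, under 1 point).

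**The case against.** **The sentence may only be loosely worded.** Categorising by degree and distribution could mean describing fibrosis along two dimensions, and the Cardiac MRI paragraph already correlates burden with the electrogram data. A reader might infer from the later sentence that categories are the only form in which fibrosis will be analysed. The documents do not establish that, and this part of the objection stands. But the Cardiac MRI paragraph names no model, so it does not override the sentence that does. On either reading the plan leaves open which form enters the regression, and the same edit settles it.

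**The loss depends on assumptions.** A reader might want to attach one cost to the choice, such as 10 to 20 points of power. The documents do not support any single figure. Degree is ordered, so unordered groups are an unlikely worst case, and with four ordered groups at a correlation of 0.5 the loss is only about 6 to 9 points.

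**The unit of analysis is not fixed.** Section 7 plans a regional metric for each kernel of atrial data as well as a global one. If fibrosis is related to regional data, patient-level power figures do not apply. This stands as a limit on the illustration.

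**Subgroup size matters more.** Even with continuous burden, 80% power needs a correlation of about 0.79 at n=10 or 0.49 at n=30. That is true and the fix does not change it, but more scans would be costly and this edit is not.

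**Conclusion.** The point holds in a limited form. The only modelling sentence for fibrosis categorises its degree without cut-points, number of groups or rationale, and it sits uneasily with the burden analysis planned earlier in the same section. Keeping burden continuous is the better method at almost no cost.

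The size of the gain is not known. At a correlation of 0.5, with n between 20 and 30, categorising costs about 22 points of power with a median split, 11 to 12 with three ordered groups and 7 to 9 with four. This assumes one bivariate-normal pair of values per patient and a two-sided 5% test.

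A reader might also infer that fibrosis burden is named in the primary objective. It is not. Section 2 speaks only of functional, structural and clinical determinants; fibrosis appears as the structural characteristic in section 1.2 and as an example in section 7. The analysis is exploratory, with no stated test or power target, so the impact is modest. This is a worthwhile correction, not a threat to the study.

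**What to change.** In section 7, under the heading on non-invasive classification, state that left atrial fibrosis burden, in its measured units, enters the regression and machine-learning models as a continuous variable. Distribution pattern should be a separate categorical term, and categories of degree should be used for description only. This brings the sentence into line with the Cardiac MRI paragraph. If categories of degree must be modelled, fix their number, cut-points and coding before the electrogram data are examined.

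In the same edit, say whether the unit of analysis is the patient or the region, and reconcile the MRI subgroup size between sections 3.2 and 7.

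The cost is a sentence or two of wording, with no new scans or patients. The downside is an assumed linear relation, which a scatter plot or a rank correlation can check.

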3.1. Study outcome measures

We will classify patients into electrophenotypes based on the invasive and non-invasive data collected. The primary outcome measure will be freedom from AF. Secondary outcome measures will be AF burden and quality of life.

[figure not shown]

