Patients undergoing AF ablation will be provided with an AliveCor device to use up to once per day and when they have symptoms to accurately monitor for recurrence of AF. They will also have holter monitoring and clinical follow up in line with routine clinical care. Patient's will be asked to complete symptom score/quality of life questionnaires up to once per month during follow up.

Patients undergoing DCCV will be followed as per routine clinical care.

Study participation will conclude after 300 patients have been recruited. Patients will be able to leave the study at any time they wish; they need only inform the research team.

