6. ASSESSMENT AND FOLLOW-UP

Patients undergoing AF ablation and the 252 lead ECG protocol will be provided with an AliveCor device to use up to once per day and when they have symptoms to accurately monitor for recurrence of AF. They will also be asked to complete symptom score (36-Item Short Form Survey Instrument (SF-36) and Atrial Fibrillation Effect on Quality-of-life (AFEQT)) questionnaires up to once per month. They will have Holter monitoring and clinical follow up in line with routine clinical care.

Patients undergoing DCCV will be followed as per routine clinical care for 1 year.

The end of study is when the last patient has completed their last follow up visit.

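### Relating outcome to electrophenotype after ablation shows prognosis, not which groups benefit more, and the DCCV patients cannot supply the missing comparator as planned

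*Combined protocol and SAP*

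**What the plan says.** **Outcomes.** Section 3.1 states: "The primary outcome measure will be freedom from AF". It adds: "Secondary outcome measures will be AF burden and quality of life". It also allows classification from both invasive and non-invasive data.

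**Analysis.** Section 7 (Outcomes) states: "Freedom from AF, AF burden and quality of life outcome data will be correlated with electrophenotype groups". The purpose given is "to investigate if certain groups benefit more from ablation than others". It names no comparator, contrast, interaction or adjustment set. Elsewhere, section 7 has a separate prognostic aim: how well the electrophenotype predicts outcome relative to conventional clinical and echocardiographic predictors.

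**Treatment and phenotype.** Under section 3.2, patients are already listed for ablation or DCCV on clinical grounds. The AF ablation protocol includes intracardiac mapping in AF (step 10), pulmonary vein isolation (step 12) and cardioversion (step 14). The DCCV protocol has surface recordings and no mapping. Section 7 takes intracardiac data as the gold standard.

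**Follow-up.** Section 3.2 says: "Patients undergoing AF ablation will be provided with an AliveCor device to use up to once per day and when they have symptoms". It asks for "quality of life questionnaires up to once per month during follow up". Section 6 says: "Patients undergoing AF ablation and the 252 lead ECG protocol will be provided with an AliveCor device", and attaches SF-36 and AFEQT to the same patients. For the others: "Patients undergoing DCCV will be followed as per routine clinical care for 1 year". No study device or questionnaire is listed for DCCV patients. Section 4.1 provides only the usual NHS assessment before the procedure.

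**The concern.** Whether some groups benefit more from ablation is a question about treatment-effect heterogeneity. A correlation between phenotype and outcome among treated patients answers a different question: who does well afterwards. A phenotype with a poor outcome may still gain as much from ablation as any other, or more.

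This matters because section 1.1 already raises the possibility that disorganised AF might be better left without ablation. A purely prognostic association could be read as support for that selection.

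The analysis carries the primary and both secondary outcome measures, and three features of the data limit it further:

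- The only non-ablation patients lack the reference phenotype and are monitored less closely.
- It is unclear which ablation patients have the device and questionnaires.
- No pre-procedure quality of life score is specified, and one cannot be recovered after the procedure.

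**Working it through.** **1. The plan's own figure.** None is attached to this analysis. Section 3 gives an enrolment of 300. Section 7 ties it to biomarker and ECG differences, without effect size, error rate or power, so it cannot be reproduced. The split between ablation and DCCV is not stated.

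**2. What outcomes after ablation can identify.** Let F1 be freedom from AF after ablation and F0 freedom without it, for phenotypes A and B.

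- Prognostic contrast: F1(A) − F1(B).
- Differential benefit: [F1(A) − F0(A)] − [F1(B) − F0(B)].

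Data from ablated patients give F1 only. With invented values:

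| Scenario | F1 A / B | F0 A / B | Gain in A | Gain in B |
|---|---|---|---|---|
| Equal benefit | 65% / 35% | 45% / 15% | 65 − 45 = 20 | 35 − 15 = 20 |
| More benefit in B | 65% / 35% | 55% / 10% | 65 − 55 = 10 | 35 − 10 = 25 |

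The observed data are the same in both rows. A larger sample would not separate them.

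**3. Whether DCCV patients can supply F0.**

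- *Phenotype:* mapping appears only in the ablation protocol. A surface-based label is possible, but the non-invasive classifier is itself to be developed in this study.
- *Allocation:* treatment is chosen clinically and no adjustment is planned.
- *Ascertainment:* ablation patients have a handheld ECG up to daily and with symptoms, plus routine Holter monitoring. DCCV patients have routine care.

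**4. Size of the ascertainment problem if the two groups were pooled or compared.** Observed freedom = 1 − recurrence × detection. Recurrence is assumed to be 50% in both groups. Section 1.1 gives 50% success for ablation of persistent AF only; no DCCV rate is given. All detection rates are assumptions.

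| Detection, ablation / DCCV | Observed freedom, ablation | Observed freedom, DCCV | Spurious gap |
|---|---|---|---|
| 0.90 / 0.80 | 1 − 0.5 × 0.90 = 55% | 1 − 0.5 × 0.80 = 60% | 5 points |
| 0.95 / 0.80 | 1 − 0.5 × 0.95 = 52.5% | 60% | 7.5 points |
| 0.90 / 0.50 | 55% | 1 − 0.5 × 0.50 = 75% | 20 points |
| 0.95 / 0.50 | 52.5% | 75% | 22.5 points |

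The direction is always against ablation.

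**5. Who holds the device.**

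| Place | Content |
|---|---|
| Section 3.2, follow-up text | Device for ablation patients generally |
| Section 6 | Device and questionnaires for ablation patients who are also in the 252 lead protocol |
| Section 3.2, 252 lead protocol | Subgroup of 50–100, having ablation or DCCV |
| Section 3.2, AF ablation protocol, step 1 | Electrodes on all ablation patients |

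If step 1 governs, sections 3.2 and 6 agree. If the subgroup definition governs, some ablation patients have no device and no questionnaires. The text does not settle which.

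**6. Quality of life.** Section 3.2 places the questionnaires in follow-up. AF duration and co-morbidities are to be tested as correlates of phenotype, and they may also affect quality of life before treatment. Follow-up scores alone cannot separate that difference from a later one.

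**7. Precision, for scale only.** Assumptions: two-sided 5%, 80% power, rates near 50%, two equal phenotypes.

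- Prognostic contrast, 2.80 × √(2 × 0.25/n per phenotype): 300 ablation patients (n = 150) give 16 points, 150 (n = 75) give 23, and 100 (n = 50) give 28.
- Phenotype-by-treatment interaction with 300 patients in four cells of 75: 2.80 × √(4 × 0.25/75) = 32 points.

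**The case against.** The strongest reply is that the plan promises little. It says it will investigate whether groups differ, and section 7 separately states a prognostic aim that needs no comparator. The primary objective in section 2 concerns the range and determinants of phenotype, not benefit from ablation. On this view the defect is one loose phrase. That is fair on tone, but the phrase is the stated purpose of the analysis of all three outcome measures, and the analysis cannot serve it.

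Several stronger readings are tempting, and the documents do not support them:

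- *The plan claims to show benefit.* It says only that it will investigate this.
- *DCCV is the planned comparator.* None is named, and no text pools DCCV patients into the outcome analysis. Nor is monitoring planned to differ by phenotype. The 5 to 22.5 point gap therefore belongs to a contrast that the plan does not name.
- *DCCV patients have no phenotype.* Section 3.1 allows non-invasive classification, and all groups give blood. They lack the reference phenotype.
- *Only 50–100 ablation patients hold a device.* That subgroup spans both treatments.
- *Baseline quality of life is excluded.* It is not specified. Section 6 does not confine the questionnaires to follow-up, and the subgroup diagram was not available to check.
- *AF burden is inflated by symptom-triggered recordings.* No text says these are pooled with scheduled ones. The burden definition is simply left open.

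**Conclusion.** The concern holds in a limited form. Followed as written, the section 7 analysis identifies prognosis after ablation. It cannot identify differential benefit, whatever the sample size, and this conclusion rests on no numerical assumption.

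DCCV patients cannot act as comparator under the present plan. If they were used that way, differential detection alone could produce a 5 to 22.5 point difference in freedom from AF. That range depends wholly on the assumed detection rates and on equal 50% recurrence. It is not an estimate of bias in the planned comparison of phenotypes.

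Within ablation patients, monitoring affects the phenotype comparison only if device access or voluntary use varies with phenotype. The unresolved eligibility text leaves the access route open. The size of any carry-over from unmeasured baseline quality of life cannot be derived from the documents.

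**What to change.** 1. In section 7 (Outcomes), change the purpose from greater benefit to whether groups *have a different prognosis after ablation*. This matches the prognostic aim already in that section.
2. Make ablation patients with an intracardiac AF map the main population for the outcome-by-phenotype analysis. Report DCCV patients separately, without pooling.
3. Reconcile the 252 lead subgroup definition, the ablation protocol's electrode step and the follow-up text in section 3.2 with section 6. State one monitoring rule for everyone in the outcome analysis, or restrict that analysis to device holders.
4. Collect SF-36 and AFEQT once before the procedure, and analyse follow-up scores by ANCOVA on baseline.

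**Cost.** A short amendment and one extra questionnaire per ablation patient. Any cost of extra devices cannot be sized, because the number of ablation patients is not stated; restricting the analysis to device holders avoids it. The outcome analysis set becomes smaller, and the conclusion weaker but supportable. Items 3 and 4 must be in place before patients are treated; items 1 and 2 change only the analysis text.
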